Primary SA1: Determine whether 24 weeks of GnRH_{AG} therapy causes a decline in physical activity when compared with placebo. Change in physical activity energy expenditure (PAEE) from baseline will be measured after 12 (secondary outcome) and 24 wk (primary outcome) of GnRH_{AG} vs placebo therapy. PAEE will be the difference between total daily EE (TEE) measured by the doubly-labeled water technique (DLW) and sleeping EE (SEE) measured by indirect calorimetry, adjusted for the thermic effect of feeding (TEF).¹⁴

H1: PAEE will decrease significantly after 12 and 24 weeks of GnRH_{AG} therapy when compared with placebo.

Secondary SA2: Determine the effects of gonadal function on multiple components of energy expenditure under free-living (DLW) and controlled (metabolic chamber) conditions, including 1) 24-h TEE measured by DLW, and 2) resting EE (REE), SEE, and TEF measured by indirect calorimetry in a metabolic chamber.

H2: When compared with placebo, GnRH_{AG} therapy will cause a decrease in TEE. The relative contributions of REE, SEE, TEF, and PAEE to the decline in TEE will be evaluated.

Secondary SA3: Determine whether the disruption of energy balance in response to GnRH_{AG} therapy leads to unfavorable changes in biomarkers of disease risk, including adiposity, insulin resistance, and inflammation. This will include the measurement of biomarkers in adipose tissue samples.

H3: When compared with placebo, GnRH_{AG} therapy will cause increases in adiposity, insulin resistance, and fasted serum inflammatory cytokines.

Secondary SA4: Because programmed exercise mitigates metabolic consequences of gonadectomy in animals, we will determine whether the bioenergetic and metabolic consequences of GnRH_{AG} in women can be

mitigated through a programmed, supervised exercise intervention (GnRH_{AG} vs GnRH_{AG}+exercise).

H4: Programmed exercise will attenuate the decrease in TEE and the increases in adiposity, insulin resistance, and inflammatory cytokines.

Exploratory Aim: To evaluate the effects of chronic sex hormone suppression and exercise on arterial stiffness and endothelial function. This preliminary data will be used for a new grant application examining the effects of exercise on modulating vascular function in E2-deficient women.

2. Research Strategy

2.a. Significance

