Chamber stay. Participants will report to the CTRC at 0700h after an overnight fast. A urine sample for DLW will be obtained, if necessary. An IV catheter will be positioned in an antecubital vein and a fasted blood sample will be obtained. Participants will enter the chamber at 0800h. A reclining chair will be positioned next to the port in the chamber through which blood samples are obtained. Participants will rest for the first hour. At 0900h, they will drink a 75-g glucose beverage and remain semi-recumbent for the next 2 hours for the TEF measurement. To mimic typical activity outside the calorimeter, two 30-min bouts of treadmill walking at 3 mph will be performed at 1500h and 1630h. This activity should produce a physical activity level (PAL; TEE/REE) of ~1.5 (unpublished observations, [name] and [name]). All urine will be collected and analyzed for urine nitrogen, urea nitrogen, and creatinine for substrate oxidation calculations. Core temperature will be measured during the chamber stay using an ingestible thermistor capsule (length 23 mm, diameter 8.6 mm) and a VitalSense telemetric monitor. TEE will be calculated as previously described.⁵³ Stepping EE will be measured during the exercise bout. SEE will be measured from 0100h to 0400h.⁸¹ Pre-study diet and exercise are known to affect 24-h fat oxidation.^{82,83} Subjects will be asked to refrain from structured exercise the day before the chamber stay. Diet will not be controlled because of the possibility that energy intake (and possibly macronutrient preference) is influenced by ovarian function. The energy composition of the diet for the chamber stay will be 30% fat, 55% carbohydrate, and 15% protein, with the 75g glucose beverage accounting for breakfast and about 25% of total energy needs, while both lunch and dinner will each account for about 30-35% of total energy needs. 'Extra' calories will be provided in the form of a snack box that participants will have free access to from the time the lunch meal is delivered until lights out. Participants will be instructed to eat what they want and that it is not necessary to eat all the food provided. This approach may provide insight on whether the suppression of ovarian function promotes hyperphagia. Data from each calorimeter stay will be evaluated for state of energy balance.

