The **rationale** for the chamber stay is to **1)** obtain a prolonged measure of basal metabolic rate for the calculation of PAEE, **2)** obtain a measure of TEE under controlled conditions, **3)** determine whether TEF is influenced by GnRH_{AG}, and **4)** determine whether EE during a specific physical task (stepping activity) is influenced by GnRH_{AG}. PAEE will be the difference between TEE measured by DLW (adjusted -10% for TEF) and SEE measured during the chamber stay, as previously described.¹⁴ The OGTT will be performed in the calorimeter to avoid a separate visit for participants and to assess whether the TEF is influenced by GnRH_{AG}.⁸⁴

Blood samples during the chamber stay. Blood samples will be obtained before and 30, 60, 90 and 120 min after glucose ingestion. These will be used for the measurement of insulin resistance (product of the glucose and insulin areas under the curve) and inflammatory cytokines (IL-6, hsCRP) for **SA3**. The assays will be performed by the CTRC core laboratories. The extent to which changes in disease risk could be explored was limited by the resources available under the P50 mechanism. Measures of insulin resistance and mild chronic inflammation were selected because of the prominent role these factors play in metabolic dysfunction.⁸⁵

Chamber stay alternative. Heavy use of the metabolic chamber for multiple research protocols has created scheduling difficulties. Subjects who cannot complete the 24-hr metabolic chamber stay in a timely manner will be offered the option of completing this alternative approach. Subjects will report fasted to the CTRC at 7:00am and will have vitals measured and an IV catheter inserted for the OGTT. At 7:30am they will consume a 75-g glucose beverage and remain semi-recumbent for the next 3 hours for the OGTT and TEF measurements. Blood samples will be drawn before and 30, 60, 90 and 120 min after glucose ingestion. The IV will be removed after the last blood sample. TEF will be measured through indirect calorimetry using the ventilated

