hood method (Parvo Medics metabolic cart). Measurements will be taken at 30-minute intervals, and each measurement will last for approximately 10 minutes. Subjects will remain in bed for the duration of the measurements, except to use the bathroom. If the subject needs to use the bathroom, this will be done immediately after a measurement, with the patient then returning to bed as soon as possible. PAEE will be calculated exactly as it is being done in chamber studies, TEE (DLW) - (RMR + TEF).

Tissue biopsies. This research project is a component (Project I) of a Specialized Center of Research (SCOR) on Sex Differences (PI, [name]) sponsored by the NIH Office of Research on Women's Health. The topic of the UCAMC SCOR is *Bioenergetic and Metabolic Consequences of the Loss of Gonadal Function*. **SCOR Project II** (PI, [name]) is a preclinical study (animals) of *Effects of Pre-existing Obesity on Consequences of the Loss of Ovarian Function*. **SCOR Project III** (PI, [name]) is a basic study (animals) on *Sex Hormones Differentially Regulate Production of Distinct Adipocyte Populations*. The tissue samples to be obtained from participants in **Project I** (below) will address specific aims from **Project I** as well as **Projects II and III**.

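### The thermic effect of feeding (TEF) is measured over 2 hours in the chamber but 3 hours on the hood, and the 24-week TEF analysis neither sets a common window nor accounts for route

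*Combined protocol and SAP*

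**What the plan says.** Secondary SA2 (section 1) lists TEF among its outcomes, as a chamber measurement: "resting EE (REE), SEE, and TEF measured by indirect calorimetry in a metabolic chamber". H2 adds that the contribution of TEF to any fall in TEE will be evaluated.

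Section 2.d.9.1 then describes two ways of obtaining TEF.

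- **Chamber stay (Visit 4).** Before the glucose, "Participants will rest for the first hour". Once the 75 g drink has been taken, at 0900h, women "remain semi-recumbent for the next 2 hours for the TEF measurement".
- **Chamber stay alternative.** This is offered to women who cannot complete the chamber stay in good time. "Subjects will report fasted to the CTRC at 7:00am and will have vitals measured and an IV catheter inserted for the OGTT". The same 75 g drink is taken at 7:30am, and women then "remain semi-recumbent for the next 3 hours for the OGTT and TEF measurements". TEF comes from a ventilated hood: "Measurements will be taken at 30-minute intervals, and each measurement will last for approximately 10 minutes".

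On the alternative route, "Blood samples will be drawn before and 30, 60, 90 and 120 min after glucose ingestion"; the chamber schedule for blood is the same. The third hour on the hood therefore serves TEF only.

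Section 2.d.9.2 repeats Visits 1 to 4 at weeks 10-12 and 22-24. Section 2.d.10 (Secondary Analyses) analyses 24-week differences in TEF in the same way as the primary outcome, with treatment group, age group and baseline value in the model.

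**The concern.** The same glucose load is followed for 120 minutes on one route and 180 minutes on the other. No section sets a common window. None says whether TEF is a cumulative amount, a mean rate or a percentage of the load. No term for route appears in the model, and no rule keeps a woman on one route across her three test periods.

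Following the stated procedures therefore puts two windows into one outcome. A woman tested in the chamber at baseline and on the hood at 24 weeks would in general show a change in TEF caused only by the window. At stake is whether a reported TEF effect, or the lack of one, can be read as physiology. The alternative section asserts equivalence with the chamber only for the PAEE calculation, not for TEF itself.

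**Working it through.** The plan gives no TEF figure to reproduce, so the check compares the two stated windows.

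**Inputs from the documents (2.d.9.1).** Chamber window 120 min; alternative window 180 min; 75 g glucose on both; blood sampling to 120 min on both. **Not given:** the time course of the response, the scale of TEF, how many women use each route, and how many change route. Everything below that depends on these is an assumption.

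**Step 1, window length.** 180/120 = 1.5, so the alternative window is 50% longer.

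**Step 2, effect on TEF with no true change.** Let A(0-T) be the area under the rise in expenditure above rest from the drink to T minutes. The cumulative ratio is R = A(0-180)/A(0-120). The mean-rate ratio is M = R x 120/180. The sloping profiles rise linearly to a peak of 1 at 60 min and then fall linearly to zero.

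| Assumed profile | A(0-120) | A(0-180) | R | M |
|---|---|---|---|---|
| Over by 120 min | any | same | 1.00 | 0.67 |
| Zero at 180 min | 30 + 45 = 75 | 75 + 15 = 90 | 1.20 | 0.80 |
| Zero at 240 min | 30 + 50 = 80 | 80 + 30 = 110 | 1.375 | 0.92 |
| Zero at 300 min | 30 + 52.5 = 82.5 | 82.5 + 37.5 = 120 | 1.45 | 0.97 |
| Constant | 120 | 180 | 1.50 | 1.00 |

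The artefact runs from nothing to +50% on a cumulative scale, and from -33% to nothing on a mean-rate scale. Its sign depends on a choice that the plan does not state.

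**Step 3, in kcal.** For an assumed 2-hour cumulative TEF of 10 to 30 kcal, a move from chamber to hood with no true change adds TEF x (R - 1): from 0 kcal (R = 1.00) to 30 x 0.50 = 15 kcal.

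**Step 4, across women.** If a fraction s moves from chamber to hood, the mean artefact is s(R - 1) and the added SD of change is |R - 1| x sqrt[s(1 - s)], both as fractions of TEF. With s assumed to be 0.20:

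- R = 1.20: mean 0.20 x 0.20 = 4%; SD 0.20 x 0.40 = 8%.
- R = 1.50: mean 0.20 x 0.50 = 10%; SD 0.50 x 0.40 = 20%.

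Moves in the other direction have the opposite sign, so they offset the mean but still add spread. Between two arms, the bias in mean change is about (s1 - s2)(R - 1), which is zero when switching is equal in both.

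**Step 5, what is not touched.** The sample size in 2.d.4 is for PAEE: SD of change = sqrt[2(1 - 0.90)] x 330 = 147.6 kcal/d. With 15 per group and a difference of 200 kcal/d, the t test using the three-group error (42 df) has 95.1% power, which reproduces the stated 95%. TEF is not an input to it. TEE by doubly-labeled water does not depend on the TEF window.

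**Step 6, after the fix.** With 0-120 min on both routes, the ratio of windows is 120/120 = 1.0.

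**The case against.** The strongest reply is that the three hours describe the length of the session and are not a derivation rule. The analyst could take the first 120 minutes from the hood, since it reads every 30 minutes. That is right about recoverability: nothing is lost, and a reader who infers that the two routes yield permanently incomparable data goes further than the documents do. But the text assigns the third hour to TEF, and nothing in the plan tells the analyst to set it aside.

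A reader might also infer that hood TEF will be some 20% to 45% higher. This holds only for a cumulative TEF whose response lasts beyond 2 hours, and the documents state neither condition. The effect may be nil, and on a mean-rate scale it reverses.

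A further tempting inference is that the treatment comparison is biased. The documents do not support it. The stated reason for the alternative is heavy chamber use by other protocols, which has no evident link to arm, and staff collecting outcomes are blinded to drug status. No section reports that women change route. What stands is that the route at follow-up is settled after randomisation, so balance is likely but not assured.

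Finally, the directional part of H2 is a fall in TEE, which the window does not affect. The evaluation of relative contributions has no stated formula, so distortion of a particular apportionment cannot be shown. The effect on TEF as an outcome in its own right remains.

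**Conclusion.** The point holds as a modest defect in a secondary outcome. The 2-hour and 3-hour windows are stated plainly and are never reconciled, and the 24-week TEF model ignores route. With no true change, a chamber-to-hood move would multiply TEF by 1.00 to 1.50 (cumulative) or 0.67 to 1.00 (mean rate) over the assumed profiles. The upper limit of 1.50 supposes that the response in the third hour is no higher than its average over the first two.

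The main consequence is noise in the TEF change. Bias between arms arises only if route use or switching is unbalanced, and the documents give no frequency for either. The window is also only one of the route differences: chamber against hood, intermittent readings on the hood, and one hour of rest before the glucose against none stated. Whether measured TEF enters PAEE depends on formulas that differ between the two parts of 2.d.9.1. Those passages must be reconciled, but that is a separate matter.

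**What to change.** In 2.d.10, with a cross-reference from 2.d.9.1:

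1. Derive TEF on both routes over 0-120 minutes after the drink, which is also the blood-sampling window. State the scale, the resting level from which the rise is counted, and how the spaced hood readings are combined. Report the third hood hour descriptively only.
2. Record the route at baseline, 12 weeks and 24 weeks, and report it by arm.
3. Add a sensitivity analysis of 24-week TEF change limited to women tested by the same route at baseline and 24 weeks, or one adjusted for route. This is needed because a common window does not remove the differences in device, sampling and pre-glucose rest.

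**Cost.** No new visits or measurements. The third hour drops out of the comparison. The sensitivity analysis has fewer women or an extra model term, which matters when the trial is planned on 15 evaluable women per group and some combinations of route and visit may be sparse. For that reason it belongs beside the main TEF analysis and should not replace it.

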
2.d. Research methods

2.d.1. Overview

This will be a randomized, double-blinded (to the extent possible), placebo-controlled intervention to determine whether the suppression of ovarian function with GnRH_{AG} disrupts energy balance by causing a decrease in PAEE. Secondary aims are to determine the effects of the suppression of ovarian function on other components of energy expenditure and on biomarkers of disease risk and whether the consequences of GnRH_{AG} can be mitigated through programmed exercise. Participants will be women who are nearing the menopausal transition based on age (42-52 y) but have normal menstrual cycle function. They will be randomized to receive monthly injections of placebo or GnRH_{AG} (leuprolide acetate, 3.75 mg) for 24 weeks. Women who receive GnRH_{AG} will be further randomized to no exercise or a supervised exercise program. Thus, the 3 treatment arms are: placebo, GnRH_{AG}, GnRH_{AG}+exercise. Although a 2x2 study design (placebo vs drug; no exercise vs exercise) was considered, this was not feasible given the resources available under the grant mechanism.

2.d.2. Outcome variables

The primary outcome (Aim 1) will be PAEE after 24 weeks of intervention. PAEE will be the difference between TEE measured by DLW and SEE and TEF, measured by indirect calorimetry. It will be assessed at baseline and after 12 and 24 weeks of intervention. The **rationale** for PAEE as the primary outcome is the dramatic decrease in PA in response to OVX in laboratory animals (Fig 1), which could be a primary trigger for subsequent changes in adiposity and metabolic function. This will be the first controlled intervention trial to determine whether an objective measure of PA decreases in response to the suppression of ovarian function in women. GnRH_{AG} therapy for 4 months or longer increases fat mass and decrease fat-free mass (FFM).^{9,10,36} One concern is that women may begin to adopt compensatory behavioral changes (e.g., decreased food intake, increased physical activity) if changes in body composition are sensed. Thus, the greatest **biologically-mediated** decrease in PAEE may occur at the intermediate testing interval (12 weeks), before measurable changes in body composition are expected to occur; this will be the primary study endpoint.

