Limitation of the follow-up testing schedule. For women assigned to the placebo treatment arm, the follow-up tests will not necessarily occur at the same point in the menstrual cycle as the baseline test. Testing will occur during specific time intervals (weeks 10-12, 22-24) to be consistent with the GnRH_{AG} arms. Because this may increase the variance of changes in bioenergetics in the placebo arm, the sample size calculations relied on conservative assumptions (e.g., ability to detect a 25% change in PAEE; use of $\rho = 0.9$; power of 95%).

2.d.10. Data analysis

General Analysis Plan. Data analysis will occur in 4 steps: **1)** Descriptive analyses (including boxplots, scatterplots, profile plots to examine change over time) will be conducted for quality assurance and to assess need for data transformation; **2)** demographic and baseline characteristics of the groups will be compared; **3)** primary and secondary analyses will be completed; and **4)** findings will be assessed for their robustness to issues including the effects of any imbalances in important baseline covariates and the effects of missing data.

Primary Analysis. The primary analysis (**SA1**) will be an intention-to-treat comparison of the differences in the change in PAEE measured after 12 weeks of placebo or GnRH_{AG} therapy. This comparison will be conditioned on the stratification variable, age group (40-46, 47-60y). Statistical inference regarding the difference between treatment groups will be based on the estimated coefficient for a treatment group indicator variable in a linear regression model with 24-week change from baseline as the response variable, and explanatory variables,

including treatment group, age group, and baseline PAEE; the latter is included to improve the precision/power of the inference about treatment differences. The conclusion about statistical significance will be drawn from the linear contrast comparing the placebo and GnRH_{AG} groups.

Secondary Analyses. To address **SA2** and **SA3**, 24-week differences in other outcome measures (24-h TEE, REE, SEE, TEF, PA by accelerometry, measurement of biomarkers in adipose tissue samples, glucose and insulin response to OGTT, serum concentrations of

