Data management will be coordinated by the PI, with direct management by the Center on Aging data manager and guidance from the study biostatisticians ([name]). Whenever possible, study data will be transferred electronically into the Center on Aging SQL database. Double entry will be used for manually entered outcome data to track entry errors. Manual data entry will use the Research Electronic Data Capture (REDCap) interface, which is a secure web application. It provides user-friendly case report forms, real-time data entry validation (e.g., for data types and range checks), audit trails, and a de-identified data export mechanism to common statistical packages. The database is hosted at the University of Colorado Development and Informatics Service Center (DISC), which will be used as a central location for data processing and management. Data back-up and security measures are those expected of an Informatics Core at a major academic research institution. Data quality checks will be ongoing, but will formally occur (e.g., checks for duplicate entries, missing data) at least annually when progress reports are prepared.

2.d.12. Timeline

Because the PI has conducted studies that used GnRH_{AG} and exercise training interventions, the regulatory approval process should be completed within 3 to 4 months and recruitment will commence shortly thereafter. The subject accrual rate will be approximately 1.5 per month over 44 months. The primary factor limiting the accrual rate is the availability of the metabolic chamber for study visits.

2.d.14. Potential Limitations

A limitation of the study design is that GnRH_{AG} therapy may not mimic the bioenergetic and metabolic

Timeline

	Year of Study				
	1	2	3	4	5
Regulatory review and approval	—				
Create data forms and database	—				
Establish quality assurance procedures	—				
Volunteer recruitment, screening, enrollment		—	—	—	
Conduct intervention and study procedures		—	—	—	
Conduct quality assurance checks		—	—	—	
Batched analysis of blood samples			—	—	
Data analysis and manuscript preparation					—

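### The primary outcome PAEE has conflicting formulas, and nothing keeps a woman on one measurement method across visits, so switching method can create a false change

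*Combined protocol and SAP*

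**What the plan says.** PAEE is defined in four places.

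- **Section 1, SA1:** the difference between TEE by doubly-labeled water and "sleeping EE (SEE) measured by indirect calorimetry, adjusted for the thermic effect of feeding (TEF"). The form of the adjustment is not given.
- **Section 2.d.2:** "PAEE will be the difference between TEE measured by DLW and SEE and TEF, measured by indirect calorimetry".
- **Section 2.d.9.1, chamber rationale:** "PAEE will be the difference between TEE measured by DLW (adjusted -10% for TEF) and SEE measured during the chamber stay".
- **Section 2.d.9.1, chamber stay alternative:** "PAEE will be calculated exactly as it is being done in chamber studies, TEE (DLW) - (RMR + TEF").

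The alternative is available to a broad group: "Subjects who cannot complete the 24-hr metabolic chamber stay in a timely manner will be offered the option of completing this alternative approach". Section 2.d.12 adds: "The primary factor limiting the accrual rate is the availability of the metabolic chamber for study visits". Section 2.d.9.2 repeats Visits 1 to 4 at weeks 10–12 and 22–24 and does not mention consistency of method. The primary model in section 2.d.10 has explanatory variables "including treatment group, age group, and baseline PAEE", with no sensitivity analysis by method.

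**The concern.** The alternative claims to match the chamber calculation, but its basal term is a different quantity. SEE is recorded asleep, from 0100h to 0400h. RMR is recorded awake under a ventilated hood for 15–20 minutes. The plan itself lists REE and SEE as separate outcomes in SA2.

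TEF is also unsettled. It could be a flat 10% of TEE or a measured response to one 75 g glucose drink, observed for 2 hours in the chamber and 3 hours under the hood. No rule turns the drink response into a daily value.

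Two things are at stake. Two analysts following different sections could compute different primary outcomes from the same data. And because the primary analysis uses change from baseline, a woman measured by chamber at one visit and hood at another carries the method offset in her change score.

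**Working it through.** **1. The plan's own power figure.** Section 2.d.4 gives SD 330, correlation 0.90, target difference 200 kcal/d and 15 per group.

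- SD of change = √(2 × (1 − 0.90)) × 330 = 147.6, which the plan rounds to 148.
- Two-sided noncentral t at 0.05, with three-group error df = 3 × (15 − 1) = 42: power 95.2%. The stated 95% reproduces.

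**2. The formulas side by side.**

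| Source | Formula |
|---|---|
| 2.d.2 | TEE − SEE − measured TEF |
| 2.d.9.1, chamber | 0.9 × TEE − SEE |
| 2.d.9.1, alternative | TEE − RMR − TEF |

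Alternative minus chamber = 0.1 × TEE − TEF − (RMR − SEE). In general this is not zero.

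**3. Size of the gap for the same woman.** These inputs are assumptions, not in the documents: TEE 2000–2400 kcal/d; RMR 5–10% above SEE; 75 g of glucose is about 300 kcal; drink TEF is 5–10% of that, or 15–30 kcal. Setting chamber PAEE at the plan's 800 gives SEE = 0.9 × TEE − 800 = 1000–1360.

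| How TEF is read in the alternative | TEF (kcal/d) | Gap (kcal/d) |
|---|---|---|
| (a) 10% of TEE carried over | 200–240 | −136 to −50 |
| (b) Drink TEF × 4 | 60–120 | −20 to +112 |
| (c) Drink TEF rate applied to the day (5–10% of TEE) | 100–240 | −136 to +52 |
| (d) Drink TEF unscaled | 15–30 | +70 to +157 |

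Examples at the extremes, both with TEE 2400 and SEE 1360:

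- (a) 2400 − 1.10 × 1360 − 240 − 800 = −136.
- (d) 2400 − 1.05 × 1360 − 15 − 800 = +157.

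The gap is zero at a TEF of 100–172 kcal/d, or 4.3–7.5% of TEE. The sign therefore depends on the missing rule.

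Reading (b) comes from the chamber diet description, "with the 75g glucose beverage accounting for breakfast and about 25% of total energy needs". That share does not fit the drink: 300/2400 = 12.5% and 300/2000 = 15%. It cannot serve as a scaling rule.

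**4. Effect on power when switching is equal across arms.** Let p be the share switching and s the offset.

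- Balanced directions: SD = √(147.6² + p × s²).
- All in one direction: SD = √(147.6² + p × (1 − p) × s²).

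The sample sizes are 15 (planned), 22 (enrolled) and 19. The last applies the 7-of-64 loss in the investigators' current study (section 2.c): 22 × 57/64 = 19.6, rounded down.

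| Scenario | SD | Power at n = 15 / 19 / 22 |
|---|---|---|
| No switching | 147.6 | 95 / 98 / 99% |
| 25% by 100, balanced | 155.8 | 93 / 97 / 99% |
| 25% by 100, one way | 153.8 | 94 / 98 / 99% |
| 50% by 150, balanced | 181.7 | 84 / 91 / 95% |
| 50% by 150, one way | 165.5 | 90 / 96 / 98% |

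**5. Bias.** The treatment contrast shifts by the between-arm difference in net switching rate times the offset. A hypothetical 20-point difference with an offset of 50–150 kcal/d gives 0.20 × 50 = 10 to 0.20 × 150 = 30 kcal/d.

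**The case against.** The strongest reply is that the effect is small. With 25% switching by 100 kcal/d, power stays at 93% or more, and with 19 to 22 completers per group even the extreme case keeps 91–95%. A bias of 10–30 kcal/d is well below 200. That stands, and it limits how serious the point is.

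The natural reading of the alternative may also be that the chamber's 10% for TEF carries over, leaving only case (a). The chamber rationale gives measured TEF its own purpose, namely whether GnRH agonist affects it. This is reasonable, but section 2.d.2 points to measured TEF, and case (a) still leaves an offset of 50–136 kcal/d. The RMR is probably the Visit 1 value, since the alternative describes no resting measurement before the drink, but the text does not say so.

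Chamber conflicts are attributed to other protocols, and outcome staff are blinded to drug status. Both make arm-related switching less likely without excluding it. Slow accrual does not itself show that women switch between visits. The general robustness step in section 2.d.10 is open-ended but does not name method. None of this reconciles the formulas.

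**Conclusion.** The concern holds and should be fixed. The definitions conflict on the face of the text, the claim that the alternative matches the chamber calculation is wrong, and no rule prevents a change score that mixes methods.

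The size cannot be established from the documents. The range of −136 to +157 kcal/d rests on assumed TEE, an assumed RMR-to-SEE ratio and assumed drink TEF. The number of women who use or switch to the alternative is not given. The likely cost is some power and an ambiguous primary outcome. Bias between placebo and GnRH agonist is possible only if switching differs by arm.

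**What to change.** Before unblinding:

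1. State one PAEE formula with one TEF rule, align SA1, section 2.d.2 and both parts of section 2.d.9.1, and remove the statement that the alternative matches the chamber calculation.
2. Compute each woman's change only from visits that use the same basal term. There are two ways, both using measurements already scheduled.
   - **Option A:** use SEE where it exists at both visits, and hood RMR at both visits for any woman who misses a chamber stay.
   - **Option B:** use 0.9 × TEE − Visit 1 hood RMR for every woman at every visit, with the SEE version as a sensitivity analysis in women with chamber data at both visits.
3. Report the number using each method by arm and visit.
4. Do not adjust for follow-up method as a covariate, because it is determined after randomisation.

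The cost is wording and recalculation, since hood RMR is taken at Visit 1 and repeated at both follow-up intervals. Option A keeps the basal term named in SA1 for women with chamber data at both visits, but leaves two basal terms in the data set. Its choice of term can also depend on events after randomisation, though each change stays within one method. Option B departs from SA1 and replaces 3 hours of sleep data with 15–20 minutes. It also takes baseline RMR in the early follicular phase, before the doubly-labeled water period. The REE results in section 2.c imply a phase difference of about 71 − 42 = 29 kcal/d, and section 2.d.9.2 acknowledges that placebo follow-up is not matched on cycle phase.

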Tissue will be obtained from vastus lateralis muscle tissue for **SCOR Project II** and abdominal and femoral subcutaneous adipose tissue for **SCOR Project I** and **SCOR Project III**. Percutaneous muscle samples will be obtained from the vastus lateralis. Following lidocaine injection, a small incision will be made in the fascia of the vastus lateralis and 100-200 mg of muscle tissue will be removed using a Bergstrom side-cut biopsy needle with suction applied. Tissue will be flash frozen with liquid N₂. Subcutaneous adipose samples will be collected from the lateral thigh region adjacent to the muscle biopsy site and the periumbilical region of the abdomen. An infusion cannula is inserted through a small skin incision (same incision as muscle biopsy for femoral collection) to infiltrate a 50-100 cm² area of subcutaneous adipose tissue with 50 ml of normal saline containing 0.0015% lidocaine (15 ml 1% lidocaine per 100 ml saline). An aspiration cannula will be used to collect 10 cc of a mixture of fluid and adipose tissue using Coleman's manual vacuum ("mini liposuction") technique.⁸⁶ Collected tissue will be separated from the fluid and processed for analysis. The incision will be closed with a suture, covered with a bandage, and an ice compress applied for 10 min.

Vascular sub-study procedures.

Resting Arterial Blood Pressure. At baseline and after Phases 2 and 3 brachial artery blood pressure will be measured both sitting (after 10 minutes of rest) and supine under quiet, comfortable ambient laboratory conditions. Blood pressure will be measured in triplicate using an oscillometric technique (Dinamap).

Arterial Stiffness. Common carotid artery diameter will be measured from the images derived from an ultrasound machine (GE Vivid i) equipped with a linear array transducer as previously described in CTSC protocols 1574, 1618, 1673 and 1466. Carotid diameter image will be analyzed using image analysis software (Carotid Analyzer). The pressure waveform and amplitude will be obtained from the common carotid artery using arterial applanation tonometry, a high-fidelity strain gauge transducer (Millar Instruments). The combination of ultrasound imaging of the common carotid artery with simultaneous applanation tonometric-obtained arterial pressure waveforms from the contralateral artery permits noninvasive determination of carotid artery compliance.

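### The lidocaine strength stated for the fat-biopsy infiltrate (0.0015%) is 87 to 100 times lower than the recipe beside it gives (0.13% to 0.15%)

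*Combined protocol and SAP*

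**What the plan says.** The instruction is under Tissue biopsies, within Visit 4 of section 2.d.9.1. Fat is taken from two places, the "lateral thigh region adjacent to the muscle biopsy site and the periumbilical region of the abdomen". Before aspiration, the operator infiltrates an area of "subcutaneous adipose tissue with 50 ml of normal saline", and the fluid is specified as "normal saline containing 0.0015% lidocaine (15 ml 1% lidocaine per 100 ml saline". The words in parentheses are the recipe for the percentage just before them.

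No other section gives a lidocaine strength. The tissue-biopsy paragraphs of section 3.1.c (risks) and section 3.2.b (protections) mention the anesthetic without a concentration. Section 2.d.9.2 repeats visits V1 to V4 at weeks 10 to 12 and 22 to 24, so the instruction can apply up to three times per participant. Section 3.1.a plans 66 participants.

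**The concern.** A percentage and the recipe that is meant to produce it should agree, and here they differ by about two orders of magnitude. Rounding cannot explain that, and neither can the choice between adding the stock to 100 ml and making it up to 100 ml.

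At stake is the preparation of a drug, not the trial's inference. Someone who prepared the fluid from the percentage would deliver about 1% of the lidocaine in the recipe, for a procedure done by cannula and suction. Someone who used the percentage to add up a participant's total lidocaine would understate the infiltrate's share by about 99%.

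**Working it through.** **Inputs**, all from the Tissue biopsies text of section 2.d.9.1:

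- Stated strength: 0.0015%, which is 0.015 mg/ml (1% w/v is 10 mg/ml).
- Recipe: "15 ml 1% lidocaine per 100 ml saline".
- Volume infiltrated: 50 ml.
- Adipose sites: two.

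**Formula.** Concentration = (stock volume × stock strength) / final volume.

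**Lidocaine in the recipe.** 15 ml × 10 mg/ml = 150 mg.

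**Attempt to reproduce 0.0015%.** The words "per 100 ml saline" can be read in two ways:

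| Reading | Final volume | Concentration | Ratio to 0.015 mg/ml |
|---|---|---|---|
| 15 ml added to 100 ml | 115 ml | 150/115 = 1.304 mg/ml = 0.130% | 1.304/0.015 = 87 |
| Made up to 100 ml | 100 ml | 150/100 = 1.500 mg/ml = 0.150% | 1.500/0.015 = 100 |

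Neither reading gives the stated figure.

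**Stock that 0.0015% would need.** 100 ml × 0.015 mg/ml = 1.5 mg, and 1.5/10 = 0.15 ml of 1% lidocaine per 100 ml, where the recipe says 15 ml.

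**Lidocaine in the 50 ml infiltrated.**

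- By the percentage: 50 × 0.015 = 0.75 mg.
- By the recipe: 50 × 1.304 = 65 mg, or 50 × 1.500 = 75 mg.
- Understatement by the percentage: 1 − 0.015/1.304 = 98.9%, or 1 − 0.015/1.500 = 99.0%.

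If 50 ml is used at each of the two sites, which is an assumption because the text does not say so, the totals are 1.5 mg by the percentage and 130 to 150 mg by the recipe.

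**A possible origin.** On the made-up-to-100-ml reading, 15 × 0.01/100 = 0.0015 g/ml. Those are the printed digits, so a percent sign placed on an unconverted fraction would account for the figure. This is an inference; the document does not show how the figure arose.

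**The case against.** The best reply is that this is a slip of notation with the working instruction intact. The recipe gives stock strength, stock volume and diluent volume, so staff can prepare the fluid without the percentage. The digit match suggests that 0.15% was intended, which makes it unlikely that the recipe is the wrong half. If the percentage were followed, the error would be towards too little anesthetic, not overdose. At the thigh, a separate lidocaine injection precedes the muscle biopsy and the fat is collected through the same incision, which partly covers the skin there. Section 3.2.b has a trained clinician perform the procedure. The tissue serves secondary biomarkers and the sister projects, and nothing in the document links lidocaine strength to those assays.

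All of this stands as a limit on how much the point matters, and it makes 0.15% the likelier correction. It does not reconcile the two figures. The separate injection is described only for the muscle biopsy, so it offers nothing at the abdominal site. The digit match also cannot replace confirmation by the person responsible for the preparation.

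**Conclusion.** The concern holds, as a minor point. The stated 0.0015% does not follow from its own recipe, which gives 0.13% if the stock is added to 100 ml and 0.15% if it is made up to 100 ml. The gap is 87-fold to 100-fold. That conclusion rests only on the recipe as printed and on 1% meaning 10 mg/ml. The figures for 50 ml use the protocol's stated volume; only the two-site totals depend on assuming 50 ml at each site.

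The documents do not establish which figure was intended, though the recipe is more plausible. The practical risk is small and runs towards inadequate numbing. Design, primary outcome, sample size and analysis are unaffected.

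**What to change.** Ask the responsible clinician which preparation is intended, then correct the sentence so that both halves agree:

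- If the stock is made up to 100 ml, state 0.15% and word the recipe as 15 ml of 1% lidocaine made up to 100 ml with saline. The printed digits point to this version.
- If the stock is added to 100 ml, state about 0.13% and word the recipe as 15 ml of 1% lidocaine added to 100 ml of saline.
- If the clinician says that 0.0015% was intended, keep it and change the stock volume to 0.15 ml per 100 ml.

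The cost is one query and one corrected line, with no change to design, sample size or analysis.
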